The aim of this study is to evaluate the effect of using coil spring and mini screw anchorage system during maxillary molars distalization.

Study methodology

Study population:

This Randomized Clinical study will be conducted on 20 patients with age ranging from 18 to 25 years, selected from the outpatient clinic of the Orthodontic Department, Faculty of dentistry, Ain Shams University.

The subjects will be selected to fulfill the following inclusion criteria:

1. Skeletal class I, or mild to moderate skeletal class II malocclusion.
2. Full cusp or end to end class II molar relationship.
3. Mild to moderate crowding in the upper dental arch and/or increased overjet.
4. Any other indication requiring maxillary molar distalization unilaterally or bilaterally.
5. Full permanent dentition with exclusion of third molars.
6. Both first and second maxillary molars are in occlusion.
7. Normal or horizontal growth pattern.
8. Non-extraction treatment plan.
9. All subjects are free from any dental anomalies as well as periodontal and systemic diseases that may influence orthodontic treatment.

Exclusion criteria:

1. Previous orthodontic treatment.
2. Severe profile convexity requiring orthognathic surgery.
3. High mandibular angle.
4. Severe molar rotation.
5. Poor oral hygiene.
6. Severe carious lesions.

Study procedure:

An informed consent will be signed by the patients before their enrollment in the current study in which the aim of the study, the methodology and possible complications will be clearly described. This research will be reviewed by research ethics committee, Faculty of dentistry, Ain Shams University.

- Full orthodontic records will be taken for patients who meet the inclusion criteria.
These records are:
 - 1- Extra-oral and intra-oral photographs.
 - 2- Orthodontic study casts.
 - 3- Panoramic radiograph: will be used to detect any dental or bone anomalies, general periodontal condition & bone level, stage of eruption & position of third molars.
 - 4- Lateral cephalometric radiograph: will be used to determine skeletal pattern & mandibular plane angle to verify fitting the inclusion criteria.
- Extra orthodontic records: Cone Beam Computed Tomography.
- The randomization will be through computer generated selection software.

Procedure:

- The maxillary first and second molars will be banded. Brackets will be bonded to the maxillary first and second premolars.

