Document Date: June 23, 2022

Three Dimensional Assessment of Maxillary Molars Following Distalization Using Two Different Approaches

A Thesis
Submitted to Faculty of Dentistry
Ain-Shams University
In Partial Fulfillment of the Requirements of
Master's Degree in Orthodontics

Faculty of Dentistry
Ain Shams University
2022

Statistical analysis

Statistical analysis was performed with SPSS 20^{®*}, Graph Pad Prism^{®**}, and Microsoft Excel 2016^{***}.

All quantitative data were explored for normality by using Shapiro Wilk Normality test and presented as means and standard deviation (SD) values. All qualitative data were presented as frequency & percentage. All data were presented in (43) tables & (38) graphs.

Tests used:

- Comparisons 2 different groups was performed by using Mann Whitney test.
- Comparisons 2 successive follow ups periods was performed by using Paired t-test.
- Comparison between quantitative continuous data (Age & Duration) was performed by Independent t-test.
- Comparison between qualitative dichotomous data (Gender) was performed by Chi square test.
- Reliability test was performed by using Intra-class Correlation Coefficient (ICC).

* Statistical Package for Social Science, IBM, Armonk, NY, USA.

** Graph Pad Technologies, San Diego, CA, USA

*** Microsoft Co-operation, Redmond, WA, USA.

* All results presented as:

I. Normality test.

II. Baseline characteristics:

- A. Age.
- B. Gender.
- C. Duration
- D. Pretreatment measurements. (Appendix IV).

III. Measurements

The following measurements were carried for both group I and group II as well as in comparison between the two groups.

A. Skeletal measurements

- 1. Skeletal antero-posterior measurements.
- 2. Skeletal vertical measurements.

B. Dental measurements

- 1. Angular
- 2. Linear

C. Soft tissue measurements.

IV. Reliability: (Appendix V)

- A. Inter-observer.
- B. Intra-observer.

I. Normality test:

Exploration of the given data was performed using Shapiro-Wilk test and Kolmogorov-Smirnov test for normality. As Listed in (Table 11) and showed in (Figure 53), it was revealed that the significant level (P-value) was shown to be insignificant as P-value > 0.05 , which indicated that alternative hypothesis was rejected, and the concluded data originated from normal distribution (parametric data) resembling normal Bell curve in pre & post measurements while P value was significant in the difference between both groups which indicated nonparametric data.

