Table (11): Normality exploration of both groups regarding all measurements:

Measurements		Group I Single Coil Spring	Group II Double Coil Spring
Skeletal.	Pre	> 0.05	> 0.05
	Post	> 0.05	> 0.05
	Difference	$< 0.05^*$	$< 0.05^*$
Dental	Pre	> 0.05	> 0.05
	Post	> 0.05	> 0.05
	Difference	$< 0.05^*$	$< 0.05^*$
Soft tissue	Pre	> 0.05	> 0.05
	Post	> 0.05	> 0.05
	Difference	$< 0.05^*$	$< 0.05^*$

* Significant difference as $P < 0.05$

[figure not shown]
[figure not shown]

Figure (53): Scattered chart represents normal bell curve of normality test.

II. Baseline characterized:

1. Age:

In group I, minimum age was (18.4), maximum was (21.2), while mean \pm standard deviation was (19.42 ± 1.03) . In group II, minimum age was (18.08), maximum was (23.17), while mean \pm standard deviation was (20.7 ± 2.24) , as presented in table (12) and figure (54).

Comparison between both groups was performed by using Independent t-test which revealed insignificant difference between them as $P > 0.05$, as presented in table (12).

Table (12): Minimum, maximum, mean & standard deviation of age in both groups:

	Min	Max	M	SD	P value
G I	18.4	21.2	19.42	1.03	0.09
G II	18.08	23.17	20.7	2.24	

N: count

Min: minimum

Max: maximum

M: mean

SD: standard deviation

[figure not shown]

Figure (54): Bar chart showing mean of age in both groups.

2. Gender:

In gender all companions were performed by using Chi square test. In group I, male (16.67%) was significantly lower than female (83.3%) as $P < 0.05$, while in group II male (33.3%) was insignificantly lower than female (66.6%) as $P > 0.05$, as presented in table (13) and figure (55).

Also, comparison between group I & II reveled insignificant difference between them in both male & female as $P > 0.05$ as presented in table (13).

Table (13): Frequency & percentage of gender distribution in both groups:

Group	Male		Female		P value
	N	%	N	%	
Group I	2	16.67%	10	83.33%	0.001*
Group II	3	33.33%	6	66.67%	0.13
P value	0.34		0.34		

N: count

%: percentage

P: probability level which is significant at $P \leq 0.05$

[figure not shown]

Figure (55): Bar chart showing percentage of gender distribution in both groups

3. Duration:

In group I, minimum duration was (5.5 months), maximum was (9.73 months), while mean \pm standard deviation was (8.03 ± 2.9) . In group II, minimum duration was (4 months), maximum was (14.9 months), while mean \pm standard deviation was (10.59 ± 3.89) .

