Comparison between both groups was performed by using Independent t-test which revealed insignificant difference between them as $P>0.05$, as presented in table (14) and figure (56).

Table (14): Minimum, maximum, mean & standard deviation of duration in months in both groups:

	Min	Max	M	SD	P value
Group I	5.50	9.73	8.03	2.90	0.09
Group II	4.00	14.90	10.59	3.89	

M: mean SD: standard deviation

P: probability level which is significant at $P \leq 0.05$

[figure not shown]

Figure (56): Bar chart showing mean of duration in months in both groups.

III. Measurements:

A. Skeletal:

1. Anteroposterior:

- Group I:**

In group I pretreatment records, post treatment records and difference between them regarding anteroposterior skeletal measurements were presented in table (15) and figure (57).

Comparison between pretreatment & post treatment records was performed by using Paired t-test which revealed insignificant difference between them in all measurements as $P > 0.05$, as presented in table (15).

Table (15): Mean & standard deviation of pretreatment, post treatment records and difference between them regarding anteroposterior skeletal measurements in group I:

Group I Anteroposterior Skeletal Measurements	Pre		Post		Difference		P value
	M	SD	M	SD	M	SD	
SNA angle	83.41	4.33	83.47	3.90	0.05	1.26	0.854
SNB angle	77.98	3.18	77.44	2.53	-0.54	1.36	0.194
ANB angle	5.50	2.11	6.07	2.53	0.57	1.72	0.273
A-NV distance	6.79	4.69	6.96	3.87	0.17	1.11	0.611
Pog-NV distance	6.06	6.44	6.02	5.32	-0.04	2.20	0.951

M: mean SD: standard deviation

P: probability level which is significant at $P \leq 0.05$

[figure not shown]

Figure (57): Bar chart showing mean of pretreatment, post treatment records and difference between them regarding anteroposterior skeletal measurements in group I.

- **Group II:**

In group II pretreatment records, post treatment records and difference between them regarding anteroposterior skeletal measurements were presented in table (16) and figure (58).

Comparison between pretreatment & post treatment records was performed by using Paired t-test which revealed insignificant difference between them in all measurements as $P > 0.05$, as presented in table (16).

Table (16): Mean & standard deviation of pretreatment, post treatment records and difference between them regarding anteroposterior skeletal measurements in group II:

Group II Anteroposterior Skeletal Measurements	Pre		Post		Difference		P value
	M	SD	M	SD	M	SD	

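### The t-test for age and duration has no stated variance assumption; Welch's test should be named because the smaller arm has the larger SD, although no printed conclusion changes

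*SAP*

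**What the plan says.** Under Tests used, the SAP says: "Comparison between quantitative continuous data (Age & Duration) was performed by Independent t-test". No variance assumption is given there or in the results sections. For both age and duration the results text reads: "Comparison between both groups was performed by using Independent t-test which revealed insignificant difference between them". Tables 12 and 14 each print P = 0.09 against a threshold of 0.05.

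The figures for age are 19.42 (SD 1.03) in Group I and 20.7 (SD 2.24) in Group II. For duration in months they are 8.03 (SD 2.90) and 10.59 (SD 3.89). Of Group I's duration the SAP also says: "minimum duration was (5.5 months), maximum was (9.73 months".

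Tables 12 and 14 give no group sizes. Table 13 (gender) does: "Group I 2 16.67% 10 83.33% 0.001" makes 12 patients, and "Group II 3 33.33% 6 66.67% 0.13" makes 9. The protocol says the study "will be conducted on 20 patients" and gives no split.

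**The concern.** The pooled t-test assumes equal variances. When the smaller group has the larger variance, pooling gives too much weight to the tighter, larger group. The standard error is then too small, and the test rejects more often than its nominal 5%. Both comparisons show this pattern: Group II has fewer patients and the larger SD for age and for duration.

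Duration is the variable of more interest. The SAP lists it among baseline characteristics, but under the protocol distalization continues until the molar correction is judged complete, so its length is a result of treatment. It is also the only between-group comparison of time in the SAP. The Group I duration row cannot be right as printed, so this test will have to be rerun. The version should be fixed before that happens.

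**Working it through.** **Inputs.** Means and SDs come from Tables 12 and 14, and n = 12 and 9 from Table 13. Two-sided testing at 0.05 is assumed, because the SAP does not state sidedness.

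**Formulas.** Pooled variance: s² = [(n1−1)s1² + (n2−1)s2²]/(n1+n2−2), with SE = √[s²(1/n1 + 1/n2)] and 19 df. Welch: SE = √(s1²/n1 + s2²/n2), with Satterthwaite df.

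**Age** (difference 20.7 − 19.42 = 1.28)
- Pooled: s² = (11×1.0609 + 8×5.0176)/19 = 2.727; SE = √(2.727×0.1944) = 0.728; t = 1.76; P = 0.0949. This rounds to the printed 0.09.
- Welch: SE = √(0.0884 + 0.5575) = 0.804; t = 1.59; df = 10.5; P = 0.141.

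**Duration as printed** (difference 10.59 − 8.03 = 2.56 months)
- Pooled: s² = (11×8.41 + 8×15.132)/19 = 11.24; SE = √(11.24×0.1944) = 1.478; t = 1.73; P = 0.0995. This rounds to 0.10 and gives the printed 0.09 only if truncated.
- Welch: SE = √(0.7008 + 1.6813) = 1.543; t = 1.66; df = 14.3; P = 0.119. The 95% CI for the difference is −0.7 to 5.9 months.

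**Error rates.** Normal data were simulated with no mean difference and with the true SDs set to the printed ones.
- Age: pooled 8.0%, Welch 5.1%.
- Duration: pooled 6.0%, Welch 5.0%.

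The variance-ratio F test gives P = 0.02 for age and 0.36 for duration.

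**Can Group I's duration SD be 2.90?** For values between 5.50 and 9.73 with mean 8.03, SD ≤ √[(9.73−8.03)(8.03−5.50)×12/11] = √4.69 = 2.17. With exactly 12 values the largest attainable SD is 2.11: four at 5.50, seven at 9.73 and one at 6.25. The smallest is 0.92, with one value at each end and ten at 8.113. So 2.90 is impossible with that range and mean.

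**If only that SD is wrong**, with both means and Group II's SD unchanged:

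| Group I SD | Pooled P | Welch P |
|---|---|---|
| 0.92 | 0.039 | 0.086 |
| 1.50 | 0.0497 | 0.091 |
| 2.00 | 0.064 | 0.098 |
| 2.11 | 0.067 | 0.100 |

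Pooled P crosses 0.05 at an SD of about 1.51. Welch stays above 0.05 throughout.

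**Sensitivity to group size.** With 10 and 10 patients, P is 0.118 pooled and 0.125 Welch for age, and 0.113 and 0.114 for duration. With 12 and 10, the pooled P values are 0.091 and 0.092. No split tried reaches 0.05 with the printed SDs.

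**The case against.** A reader might infer that the choice of t-test decides whether the duration difference is significant. The documents do not support that. On the printed figures both versions leave both comparisons non-significant, and Welch only moves the P values further from 0.05. A disagreement needs a Group I SD below about 1.5, and the documents do not give one.

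Nor can a reader safely infer that duration was tested with pooled variances. That match relies on the SD of 2.90, which is impossible beside its own range and mean, and it also needs truncation. If only the SD is misprinted and the P value came from the patient data, the printed 0.09 agrees with Welch (0.086 to 0.100 over the possible SDs) and not with pooled (0.039 to 0.067). If instead the SD is right and the range is wrong, the pooled match survives, but nothing becomes significant.

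Three further objections carry weight. The error rates treat SDs from 12 and 9 patients as the true ones, and unequal variance is not established for duration. The group sizes are borrowed from Table 13. And age is only a baseline check in a randomised study, so an 8% error rate there affects no treatment conclusion.

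What stands is that the version is unstated, the age P value points to pooling in the configuration where pooling is liberal, and Welch costs almost nothing even if the variances are equal.

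**Conclusion.** The point holds as a minor one about an unspecified method. For age, the pooled test is inferred from the printed P value with n = 12 and 9; its error rate is about 8% if the true SDs resemble the observed ones. For duration, the excess on the printed figures is about one percentage point, and the version used cannot be determined until the Group I row is corrected.

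The reported finding of no significant difference stands for both variables under either test. The larger defect is the impossible Group I SD in Table 14. The choice of test would matter to the conclusion only under a further condition: a corrected SD below about 1.5 with the means and Group II's figures unchanged. If the mean or range turns out to be the wrong entry, that condition may not arise.

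**What to change.** - Check Group I's duration mean, SD, minimum and maximum, and the printed P value, against the patient data, and correct whichever is wrong.
- In Tests used, name Welch's unequal-variance t-test for age and duration, two-sided.
- Reprint both P values: age becomes about 0.14, and duration is recomputed from the corrected patient data. Show n in Tables 12 and 14.
- Report the difference in mean duration with its Welch 95% CI. The interval of −0.7 to 5.9 months above is provisional, because it uses the SD of 2.90.

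The cost is one line in the SAP, a rerun of two tests, and slightly larger P values than the pooled test gives.

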SNA angle	83.64	4.14	83.62	4.15	-0.02	1.07	0.952
SNB angle	79.27	3.08	79.13	3.03	-0.14	1.24	0.735
ANB angle	4.36	1.72	4.49	1.63	0.12	0.54	0.517
A-NV distance	7.44	3.13	7.09	3.00	-0.35	0.74	0.195
Pog-NV distance	8.10	3.71	7.31	3.26	-0.79	2.04	0.277

M: mean SD: standard deviation

P: probability level which is significant at $P \leq 0.05$

[figure not shown]

Figure (58): Bar chart showing pretreatment, post treatment records and difference between them regarding anteroposterior skeletal measurements in group II.

- **Comparison between both groups:**

Comparison between group I & II regarding difference between pretreatment & posttreatment records of anteroposterior skeletal measurements was performed by using Mann Whitney test which revealed insignificant difference between them regarding all measurements, as presented in table (17) and figure (59).

Table (17): Comparison between both groups regarding anteroposterior skeletal measurements:

Difference Anteroposterior Skeletal Measurements	Group I		Group II		P value
	MD	SD	MD	SD	
SNA angle	0.05	1.26	-0.02	1.07	0.81
SNB angle	-0.54	1.36	-0.14	1.24	0.75
ANB angle	0.57	1.72	0.12	0.54	0.75
A-NV distance	0.17	1.11	-0.35	0.74	0.24
Pog-NV distance	-0.04	2.20	-0.79	2.04	0.11

MD: mean difference

SD: standard deviation

P: probability level which is significant at $P \leq 0.05$

[figure not shown]

Figure (59): Bar chart showing comparison between both groups regarding anteroposterior skeletal measurements.

2. Vertical:

- **Group I:**

In group I pretreatment records, post treatment records and difference between them regarding vertical skeletal measurements were presented in table (18) and figure (60).

Comparison between pretreatment & post treatment records was performed by using Paired t-test which revealed insignificant difference between them in all measurements as $P > 0.05$, as presented in table (18).

Table (18): Mean & standard deviation of pretreatment, post treatment records and difference between them regarding vertical skeletal measurements in group I:

Group I Vertical Skeletal Measurements	Pre		Post		Difference		P value
	M	SD	M	SD	MD	SD	
PP-SN angle	8.66	3.09	8.96	3.81	0.31	0.91	0.425
ANS-Me distance	63.77	4.78	63.81	5.66	0.04	1.43	0.924
MP-SN angle	36.91	4.09	36.76	4.20	-0.15	0.61	0.265

M: mean

SD: standard deviation

MD: mean difference

P: probability level which is significant at $P \leq 0.05$

[figure not shown]

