Comparison between pretreatment & post treatment records was performed by using Paired t-test which revealed insignificant difference between them in all measurements as $P > 0.05$ except U1-FHP and U5-FHP (Post was significantly higher than prerecord) as $P < 0.05$, as presented in table (21).

Table (21): Mean & standard deviation of pretreatment, post treatment records and difference between them regarding anteroposterior angular dental measurements in group I:

Group I Anteroposterior Angular Dental Measurements	Pre		Post		Difference		P value
	M	SD	M	SD	MD	SD	
U1-NA	25.83	9.57	26.27	10.17	0.44	1.88	0.437
U1-FHP	123.54	12.59	124.50	12.88	0.97	1.46	0.042*
U4-FHP	102.14	9.64	103.24	11.70	1.10	4.80	0.444
U5-FHP	96.83	11.01	101.88	13.25	5.06	6.02	0.014*
U6-FHP	94.43	8.90	89.70	9.02	-4.72	9.69	0.119
U7-FHP	87.70	10.16	82.83	8.09	-4.87	8.16	0.063

M: mean

SD: standard deviation

MD: mean difference

P: probability level which is significant at $P \leq 0.05$

[figure not shown]

Figure (63): Bar chart showing mean of pretreatment, post treatment records and difference between them regarding anteroposterior angular dental measurements in group I.

- **Group II:**

In group II pretreatment records, post treatment records and difference between them regarding anteroposterior- angular- dental measurements were presented in table (22) and figure (64).

Comparison between pretreatment & post treatment records was performed by using Paired t-test which revealed insignificant difference between them in all measurements as $P > 0.05$ except U4-FHP and U5-FHP (Post records were significantly higher than prerecords), and U6-FHP (Post record was significantly lower than prerecord) as $P < 0.05$, as presented in table (22).

Table (22): Mean & standard deviation of pretreatment, post treatment records and difference between them regarding anteroposterior angular dental measurements in group II:

Group II Anteroposterior Angular Dental Measurements	pre		post		Difference		P value
	M	SD	M	SD	MD	SD	
U1-NA	16.88	4.94	17.05	5.79	0.18	0.85	0.67
U1-FHP	114.61	4.00	115.05	4.83	0.43	0.83	0.44
U4-FHP	105.26	5.30	109.68	4.81	4.42	5.18	0.034*
U5-FHP	102.27	4.80	108.52	5.79	6.25	5.34	0.008*
U6-FHP	97.77	1.80	84.23	9.21	-13.54	8.61	0.002*
U7-FHP	88.47	8.81	80.17	9.62	-8.30	0.81	0.077

M: mean

SD: standard deviation

MD: mean difference

P: probability level which is significant at $P \leq 0.05$

[figure not shown]

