Figure (73): Bar chart showing mean of pretreatment, post treatment records and difference between them regarding anteroposterior linear dental measurements in group II.

- **Comparison between both groups:**

Comparison between group I & II regarding difference between pretreatment & posttreatment records of anteroposterior - linear dental measurements was performed by using Mann Whitney test which revealed insignificant difference between them regarding all measurements except U1-tip/S Ver (Group I was significantly lower than group II) as $P <0.05$, as presented in table (32) and figure (74).

Table (32): Comparison between both groups regarding anteroposterior - linear dental measurements:

[figure not shown]
Difference Anteroposterior Linear Dental Measurements	Group I		Group II		P value
	MD	SD	MD	SD	
U1-tip/S Ver	0.02	0.47	0.59	0.13	0.002*
U1-apex/ S Ver	-0.02	1.21	0.43	0.08	0.28
L1-tip/S Ver	-1.16	2.50	-0.54	1.61	1
U4-tip/S Ver	1.06	1.17	1.11	1.76	0.97
U4-apex/S Ver	2.59	1.64	1.79	1.19	0.31
U5-tip/S Ver	1.40	1.00	1.88	1.49	0.71
U5-apex/S Ver	1.86	1.55	1.37	1.58	0.71
MBc6/S Ver	-3.78	1.31	-4.51	3.39	0.8
U6-apex/S Ver	-2.78	1.64	-2.12	2.52	1
MBc7/S Ver	-3.26	1.55	-5.32	3.62	0.12
U7-apex/S Ver	-2.50	2.45	-2.40	0.98	0.86
overjet	1.19	2.43	0.85	1.25	0.75

SD: standard deviation

MD: mean difference

P: probability level which is significant at $P \leq 0.05$

Figure (74): Bar chart showing comparison between both groups regarding anteroposterior linear dental measurements.

b. Vertical

- Group I:**

In group I pretreatment records, post treatment records and difference between them regarding vertical- linear- dental measurements were presented in table (33) and figure (75).

Comparison between pretreatment & post treatment records was performed by using Paired t-test which revealed significant difference between them in all measurements as $P < 0.05$ except overbite as there was insignificant difference between pre & post as $P > 0.05$. In U1-tip/PP, pre was significantly lower than post, while in U4-tip/PP, U5-tip/PP, MBc6/PP, MBc7/PP and L1-tip/PP pre was significantly higher than post as $P < 0.05$, as presented in table (33).

Table (33): Mean & standard deviation of pretreatment, post treatment records and difference between them regarding vertical - linear dental measurements in group I:

Group I Vertical Linear Dental Measurements	Pre		Post		Difference		P value
	M	SD	M	SD	MD	SD	
U1-tip/PP	27.68	3.67	27.86	3.67	0.18	0.52	0.005*

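### SAP Table 11 reports the pre-to-post change as non-normal in both groups, yet all 18 within-group tables use the paired t-test, which assumes that same change is normal

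*SAP*

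**What the plan says.** Under 'I. Normality test' the SAP reports that pre and post measurements passed, "while P value was significant in the difference between both groups which indicated nonparametric data". Table 11, titled "Normality exploration of both groups regarding all measurements", gives the detail. For skeletal, dental and soft tissue measurements, in each group's own column, Pre and Post are above 0.05 and Difference is below 0.05.

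'Tests used' assigns the within-group test: "Comparisons 2 successive follow ups periods was performed by using Paired t-test". The results follow it. For Table 15, for example: "Comparison between pretreatment & post treatment records was performed by using Paired t-test which revealed insignificant difference between them in all measurements". The text introducing each of the other 17 within-group tables (16, 18, 19, 21, 22, 24, 25, 27, 28, 30, 31, 33, 34, 36, 37, 39, 40) also names the paired t-test.

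Between groups, the same change is given a rank test. Table 17 compares the groups "regarding difference between pretreatment & posttreatment records of anteroposterior skeletal measurements was performed by using Mann Whitney test". No paired rank test is named anywhere, and no reason is given for treating the change as non-normal in one comparison and normal in the other.

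**The concern.** A paired t-test is a one-sample t-test on the within-patient change. It needs that change to be roughly normal; whether the pre and post values are normal separately does not matter. The SAP checked the right variable, reported that it failed, acted on this between groups and ignored it within groups. With 12 and 9 patients, large-sample theory gives little protection.

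At stake are the per-arm statements on tipping, rotation and vertical and transverse tooth movement. Of the 96 within-group P values, 41 are printed at or below 0.05 (23 in Group I, 18 in Group II). Labels near the threshold are the most open to change in either direction: Group I U1-FHP 0.042 and U7-FHP 0.063 (Table 21), Group II U7 crown inclination 0.047 (Table 28) and overbite 0.053 (Table 34). Whether those particular changes are non-normal is not reported.

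**Working it through.** **Inputs.** Table 13 gives n = 2 + 10 = 12 in Group I and 3 + 6 = 9 in Group II. Mean and SD of change and P come from the within-group tables. Alpha is 0.05; two-sided testing is assumed, because the SAP does not state it.

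**1. Which variable failed.** The prose speaks of a difference between both groups, but Table 11 has a separate Difference entry for each group. That can only be the pre-to-post change, which is also how the result tables use the word.

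**2. Reproducing the SAP's figures.** t = mean change / (SD / √n), df = n − 1.
- Table 22 U6-FHP: −13.54 / (8.61 / 3) = −4.72, df 8, P = 0.0015 (printed 0.002).
- Table 34 overbite: 1.11 / (1.47 / 3) = 2.27, df 8, P = 0.053 (printed 0.053).
- Table 21 U7-FHP: 4.87 / (8.16 / √12) = 2.07, df 11, P = 0.063 (printed 0.063).

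Allowing ±0.005 in each printed mean and SD, 67 of 96 rows reproduce as paired t-tests. Tables 16, 21, 24, 27, 28, 37, 39 and 40 do so in full.

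**3. Not a slip in naming.** The smallest exact two-sided signed-rank P at n = 9 is 2/2⁹ = 0.0039. Five printed Group II values are lower: Table 22 U6-FHP 0.002; Table 25 U5-MSP 0.001; Table 31 U4-apex 0.002, MBc7 0.002 and U7-apex 0.000. An exact signed-rank test cannot give these, so they must change if it is used. They could still fall below 0.05.

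**4. Reach of Table 11.** It has one threshold entry per family and group, covering 8 skeletal, 37 dental and 3 soft tissue measurements (48 × 2 = 96 rows). It does not say which rows fail or by how much.

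**5. What changing the test does.** Simulated rejection of a true null at nominal 5%, n = 9 and 12, with assumed shapes because the real ones are not given:

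| Shape of change | Paired t | Signed-rank |
|---|---|---|
| Symmetric, heavy tails | 3.2–3.4% | 3.9–4.3% |
| Lognormal, mean zero | 15–17% | 14–17% |
| Lognormal, median zero | 5.0–7.2% | 5.1–6.7% |

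The t-test is conservative under symmetric heavy tails. Under skew the two tests err alike. These figures describe the tests, not this trial.

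**6. Printed figures that need a separate check.** In 29 rows P does not follow from the printed change: 9 in Table 30, 6 in Table 33, 3 in Table 36, 1 in Table 15, 2 in Table 18, and 8 in Group II (Tables 19, 22, 25, 31 and 34). The introduction to Table 33 reads "Comparison between pretreatment & post treatment records was performed by using Paired t-test which revealed significant difference between them in all measurements" apart from overbite, but 6 of its 7 P values do not reproduce. Table 30 prints a P of 78.77, which is that row's pre mean.

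Nine of the 29 cross 0.05:
- Group I: Table 30 U4-tip (printed 0.124, computed 0.009); Table 33 U1-tip/PP (0.005, 0.26) and L1-tip/PP (0.008, 0.31); Table 36 U4 (0.438, 0.001).
- Group II, all computed below 0.001: Table 22 U7-FHP (printed 0.077); Table 25 U7-MSP (0.057); Table 31 U1-tip (0.12) and U1-apex (0.25); Table 34 U1-tip/PP (0.16, reading its SD as 0.09).

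In all eight Group II rows, and in none of the other 88, the printed SD of change equals post SD minus pre SD within 0.01, ignoring sign. Table 22 U7-FHP: 9.62 − 8.81 = 0.81. Table 25 U7-MSP: 13.42 − 6.55 = 6.87. Table 34 U1-tip/PP: 3.19 − 3.27 = −0.08, printed as an SD of −0.09. There the SD may be the wrong figure rather than P.

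Table 32 states that its comparison "regarding difference between pretreatment & posttreatment records of anteroposterior - linear dental measurements was performed by using Mann Whitney test". For U1-tip/S Ver, a pooled t-test on the printed summaries gives variance (11 × 0.47² + 8 × 0.13²) / 19 = 0.135, standard error √(0.135 × (1/12 + 1/9)) = 0.162, t = (0.02 − 0.59) / 0.162 = −3.52, df 19, P = 0.0023; printed 0.002. Five more labelled Mann-Whitney also match: PP-SN 0.662 (printed 0.66), U1-NA 0.705 (0.70), U1-FHP 0.334 (0.33), U1-apex/S Ver 0.282 (0.28) and U1-tip/PP 0.616 (0.61, within input rounding, SD read as 0.09). All six are among the eight rows with the SD anomaly. Three other rows of 48 also fall within rounding, possibly by chance.

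**The case against.** The strongest reply is that no harm is shown. The step 5 comparison finds little gain in type I error from signed-rank, and the randomised comparison lies elsewhere. Both points stand. They limit the weight of the point but do not remove the contradiction. A justification of the t-test would need normality results per measurement, and the SAP's only evidence points the other way.

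A second reply is that Table 11 cannot support a change to 96 rows, so the authors should print normality per measurement and then justify or replace the t-test. It is true that Table 11 does not show all 96 changes to be non-normal. But choosing the test row by row from a normality test on 9 or 12 values would add another data-driven step. One test for all rows is simpler.

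A third reply is that the non-reproducing figures are not test-choice errors. That is correct. They are listed separately and lend this point no weight.

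A reader might infer that the within-group significant findings are false, or that the t-test overstated significance. The documents do not support this: the direction depends on shapes that are not reported, and no patient-level changes are given. Nor does "except U4-FHP and U5-FHP (Post records were significantly higher than prerecords), and U6-FHP (Post record was significantly lower than prerecord" (Table 22) become wrong because U6-FHP lies below the signed-rank minimum; only its P value must change.

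**Conclusion.** The contradiction holds: 6 of 6 cells in Table 11 flag the change, and 18 of 18 within-group tables use a test that assumes the change is normal. It should be corrected. Its effect on any single row, the direction of error and any changed conclusion are unknown. The only certain numerical effect of an exact signed-rank test is on five Group II P values, and their labels may stay. This rests on reading Difference as the pre-to-post change, and on n = 12 and 9 in every row.

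It would be too strong to say that signed-rank repairs skewed data, since it does not. It would also be too strong to say that the between-group results are untouched: six of them match a pooled t-test, including Table 32 U1-tip/S Ver, the only significant result in that table. A match on summaries does not prove which test was run. It is reason to check.

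**What to change.** In 'Tests used', name the Wilcoxon signed-rank test for all within-group comparisons. Beside mean and SD, report the Hodges-Lehmann estimate with its 95% CI, labelled as the pseudomedian because it is not the median under skew. Keep the paired t-test as a sensitivity analysis and flag every row where the verdict differs. Print normality per measurement and group as description only. Label the re-analysis post hoc, since results are already printed.

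The cost is one changed line, 96 rows re-run from existing data, and 18 tables with their text re-issued. The test would be chosen after results were seen. Some power is lost where changes are in fact normal: simulated at a shift of 0.8 SD, from 56% to 49% at n = 9 and from 71% to 67% at n = 12.

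As a separate task, check and correct from source data the 29 within-group rows, the eight Group II SDs (which lie within those 29 rows) and the six between-group P values. Changing the name of the test does not repair them.
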